2. LIST OF ABBREVIATIONS

AE	Adverse event
BMI	Body mass index
CKC	Closed Kinetic Chain
CLIA	Clinical Laboratory Improvement Amendments
CMP	Comprehensive metabolic panel
CPC	Cancer Protocol Committee
CRF	Case report form
CSCS	Certified Strength and Conditioning Specialist
DEXA	Dual energy x-ray absorptiometry
DSMB	Data safety and monitoring board
eCRF	electronic case report form
EPOC	Excess post-exercise oxygen consumption
FDA	Food and Drug Administration
GCP	Good clinical practice
ICH	International Conference on Harmonization
FACT-B4	Functional Assessment of Cancer Therapy - Breast
FMS	Functional Mobility Screen
IRB	Institutional Review Board
MET	Metabolic equivalent of task
NSCA	National Strength and Conditioning Association
OARC	Office of Audit, Risk and Compliance
OKC	Open kinetic chain
PI	Primary investigator
QOL	Quality of Life
RDSP	Research Data Security Plan
SAE	Serious adverse event
SOC	Standard of Care
SOP	Standing operating procedures

3 PROTOCOL SYNOPSIS

3.1 Purpose:

This protocol seeks to analyze patient outcomes of the standard of care, monitored group exercise regimen of high-load resistance training and functional exercises with compound movements under close supervision on women who have been treated for breast cancer.

Primary Objective

- 1 Determine safety and feasibility measured by exercise compliance.

Exploratory Objectives

- 1 Determine changes in functional mobility testing changes at baseline, throughout, post-exercise assessment and 1 year after exercise assessment.
- 2 Determine quality of life at baseline, throughout, and post- exercise assessment
- 3 Determine changes in strength and load lifted at baseline, throughout, post-exercise assessment, and 1 year after exercise assessment.
- 4 Determine changes in resting metabolic rate at baseline, throughout, post- exercise assessment, and 1 year after exercise assessment.
- 5 Determine changes in body composition at baseline, throughout, post- exercise assessment and 1 year after exercise assessment, including body mass, fat mass, fat-free mass, % fat, and % fat-free mass.

Hypotheses

In this study, we hypothesize that an observed exercise regimen utilizing high-load resistance training initiated during or after cancer treatment is safe and feasible in women and may improve functional mobility, body composition, and resting metabolic rate.

3.2 Background and Significance:

Obesity is a risk factor for both breast cancer and disease recurrence after treatment.¹ Furthermore, weight gain during and after treatment for breast cancer is associated with a higher risk of recurrence, distant metastases, and death.² Yet, most women gain significant weight during and after breast cancer treatment, potentially compromising outcomes.

Contrary to these findings, activity levels have been repeatedly associated with a lower risk of breast cancer incidence, improved outcomes after breast cancer treatment, and improved breast cancer-specific and overall survival.³ The majority of breast cancer survivors do not meet adequate daily activity level recommendations, potentially compounding issues with weight gain during and after breast cancer treatment.⁴ As a result, attempts are underway to both quantify and increase activity levels during treatment and survivorship.⁵ Furthermore, and based on these findings, several areas of

research have attempted to analyze both diet and exercise regimens in women with breast cancer to reduce weight. Beyond solely assessing weight gain, other data reveal a close association between several metabolic factors and poorer outcomes after breast cancer treatment, including elevated serum glucose, decreased insulin sensitivity, elevated serum insulin, increased inflammatory factors, and decreased muscle mass.^{6–8} These factors can be generally improved through specific targeted exercise training, suggesting metabolic benefits of exercise beyond simple weight loss. Furthermore, as resistance training improves strength, muscle hypertrophy, and body composition, and leads to physical and cellular changes that appear to counter these metabolic perturbations – often unrelated to changes in overall weight – such training may be a prudent strategy to improve measurable variables associated with breast cancer specific and overall health benefit.^{9–11} However, this approach differs from current exercise strategies that often aim to elicit cardiac benefits and calorie deficits through aerobic and extended activity that involves intermediate to low intensity exercises.¹²

Moreover, studies in non-cancer populations reveal that exercise is generally minimally effective for weight loss, and specifically fat loss, when unaccompanied by other health changes.¹³ Simply relying on aerobic exercise to induce caloric deficit for weight loss in the oncologic setting may be concerning in as it can lead to loss of lean mass and muscle tissue,¹⁴ and the potential metabolic and functional benefits that accompany both. Studies reveal that resistance training requiring more intense effort may help support lean mass maintenance or even muscle gains during weight loss, which has been shown to simultaneously increase resting metabolic rate to increase fat oxidation and improve body composition.^{11,15} Such changes may be more advantageous in the oncologic setting than previous exercise strategies.

For example a recent randomized trial of an unobserved home aerobic exercise regimen revealed no improvement in physical functioning in women with metastatic breast cancer, assessed via an array of physical tests.¹⁶ Another recent study in overweight women with breast cancer utilizing a 52-week, home-based exercise program consisting of lightweight strength and resistance training twice per week and 180 minutes of walking per week revealed no weight loss.¹⁷ Additionally, no improvement in aerobic fitness or strength tests was experienced by the women in the exercise group. Progression in resistance load during resistance training in the majority of studies has been slow with low loads to avoid exacerbating lymphedema.¹⁸ Yet, multiple studies have now confirmed no increase, and potentially improvement, in lymphedema in women undergoing resistance training after breast cancer treatment.^{17,19–21} For safety measures, many home exercise programs in breast cancer patients also utilize light-weight free-weights or open kinetic chain (OKC) movements where the body is fixed and the distal extremities are mobile (as in arm curls), both of which can often limit activation of core and accessory muscles, leading to a less intense regimen that may limit functional and mobility benefits and hypertrophy.^{22,23} Closed kinetic chain (CKC) exercises involve fixation of the distal aspect of the extremity (as in the squat), as opposed to proximal isolation (with OKC), therefore requiring involvement of multiple joints and co-contraction of multiple

simultaneous muscles to stabilize the body during movement, also known as compound exercises. Such CKC exercises include lunges, squats, deadlifts, and power cleans; on the contrary, examples of OKC exercises are bench press, seated leg curls and extensions, and machine curls. CKC and compound exercises also mimic athletic movements, thus positively impacting mobility and function.

Studies in non-cancer patients reveal that resistance training routines that expose muscle tissue to extensive mechanical tension with subsequent muscle damage and metabolic stress promote training-induced muscle growth.²⁴ Additionally, more intense and heavier weight lifting regimens have been consistently shown to improve several factors associated with health, including: 1) Improved strength and fitness and decreased risk of injury, 2) Increased muscle mass and corresponding decrease in inflammation,²⁵ 3) Enhanced insulin sensitivity, elevated resting metabolic rate, and decreased risk of diabetes,⁴ 4) Improved mobility and overall health,²⁶ and 5) Increased bone mineral density.²⁷ Furthermore, resting metabolic rate, which comprises the majority of daily total energy expenditure, is proportional to muscle mass.²⁸ Additionally, excess postexercise oxygen consumption (EPOC), or the continued enhanced metabolic effect after the completion of exercise, is enhanced via strenuous resistance training compared with aerobic training alone.²⁹

While weight training has clear advantages over aerobic training for improving body composition and several measurable metabolic variables, there have been barriers to its implementation in exercise regimens for the breast cancer patient, including concerns of safety and lymphedema risk.³⁰ However, as stated above, these risks have been largely disproved by the current available research.³¹ Adverse effects (AEs) reported in prior exercise studies include typical self-limiting musculoskeletal issues, including muscle strains, joint and back pain, shin splints, and tendinitis.³² Overall, AEs are minimal. Furthermore, an observed environment with supervision by trained exercise personnel can further reduce the risk of injury,^{33,34} as can adaption of a workout regimen that accounts for individuals' functional movement abilities, mobility, and function.³⁵

3.3 Rationale:

To date, the majority of exercise intervention studies for women with breast cancer after treatment focus on aerobic exercise regimens and/or low to moderate-intensity resistance training. Additionally, the components of resistance training often rely on isolated and open kinetic chain exercises utilizing light weights and high repetition schemes that may not be optimal for hypertrophy and improvement of functional movements.³⁶ These regimens have generally been implemented with two major goals: 1) Provide weight reduction, 2) Increase energy expenditure measured via metabolic equivalent of task (MET). Such goals are based on significant literature revealing improved outcomes after breast cancer treatment in physically active women and worse outcomes in women who gain weight during and after treatment.² However,

mechanistically, it is unclear if these strategies are most prudent to improve health and breast cancer-specific outcomes.³⁷

There is a paucity of data utilizing and testing multiple-joint, closed kinetic chain, and compound exercises that rely on full body movements with the goal of improving strength, hypertrophy, and functional movement patterns in women after breast cancer treatment. This remains a concerning gap in the literature, as multiple studies in non-cancer populations have revealed body composition and metabolic improvements following such weight training regimens. Additionally, studies reveal that observed exercise programs lead to enhanced strength gains and hypertrophy,³⁸ and successful exercise interventions tend to be those that involve direct supervision.³⁹ Finally, many of the exercise regimens tested include prolonged exercise regimens like treadmill and aerobic sessions lasting 90 minutes or more. More intense weight training generally lasts a fraction of this and may therefore serve as a time-effective method of exercise.

Thus, this protocol will attempt to analyze patient outcomes of an observed exercise regimen utilizing high-load resistance training via compound CKC and functional resistance exercises with the goal of improving physical and metabolic function, mobility, muscle mass, and body composition in women previously treated for breast cancer utilizing guidelines from the National Strength and Conditioning Association (NSCA).

3.4 Design and Procedure:

Feasibility and safety single-arm registry study in subjects with newly diagnosed ductal carcinoma in situ (DCIS) or invasive carcinoma of the breast.

3.5 Selection of Subjects and Sample Size:

Women ages 20-89 treated for ductal carcinoma in situ or invasive carcinoma will be considered for this trial.

The accrual goal is 43 subjects to achieve a sample size of 40 subjects, allowing for enrolled subjects who are unable to be complete the exercise program. Estimated accrual and completion time is approximately 2 years.

3.6 Duration of Study:

Subjects will be on study for an approximate 15 months, with the exercise program encompassing 12 weeks and an assessment following 1 year after the exercise program. Thereafter subjects will continue to be followed by the treating medical oncologist and/or radiation oncologist per standard of care (SOC) for follow up care but utilizing the data for research purposes.

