6. PATIENT ASSESSMENTS

Table 1: Participant Assessments

Assessment	Screening	Baseline Assessments (Prior to Program)	During Exercise Program	At Exercise Program Completion	1 Year After Exercise Program Completion
Consent	X				X ^f
History/Physical	X				
Weight, height, and BMI	X			X	X
Body Composition Assessment ^a		X		X	X
Resting Metabolic Rate Assessment		X		X	X

QOL and Exercise Forms ^b		X		X	X
Strength Assessment ^{c,d}		X	X	X	X
Mobility Assessment ^c		X		X	X
Compliance ^e			X		

- a To calculate lean and fat mass and percentages, and total energy expenditure (kcal/day) SOC
- b EQ-5D-5L, and Leisure-Time Exercise Questionnaire SOC
- c Functional Mobility Survey and Y-balance test, includes grip strength SOC
- d Will also occur periodically throughout program to adjust exercise regimen SOC
- e Attendance collected at each workout
- f Verbally reconsent to use SOC data for research purposes

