7. STATISTICAL METHODS AND DATA ANALYSIS

7.1. Analysis of Safety

Safety will be continually assessed during each workout regimen by the exercise physiologist, and adjustments will be made to exercise performance during the workout to increase safety as per standard of care.

The AEs will be reviewed and assessed by the PI and reported per AHN IRB reporting requirements. Accidental disclosure of confidentiality is the only adverse event that would occur.

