Subject names or identifiers will not be used in reports, presentations at scientific meetings, or publications in scientific journals.

Data Collection:

The following data will be stored in the secure database:

- Age
- Diagnosis
- Weight, height, and BMI
- Comorbid medical conditions
- Surgical procedure for breast cancer or orthopedic procedures
- Type of hormonal therapy
- Body composition at start/completion (body fat percentage, % fat-free mass, fat mass, fat-free mass, body mass)
- Resting metabolic rate at start/completion
- Exercise details (specific exercise, repetitions, weight, load lifted)
- FMS and Y-balance test
- Grip strength at start/completion
- QOL forms (EQ-5D-5L)
- Godin Leisure-Time Exercise Questionnaire
- Adherence rates (percentage classes)
- Assessments that are SOC

10.5 Protocol Amendments:

All protocol amendments must be initiated by the Principal Investigator and approved by the IRB prior to implementation. IRB approval is not required for protocol changes that occur to protect the safety of a subject from an immediate hazard. However, the Principal Investigator must inform the IRB and all other applicable regulatory agencies of such action immediately.

10.6 Records Retention:

The Principal Investigator will maintain study-related records for the longer of a period of at least six years after study completion, or per AHN policy, whichever is more strict.

APPENDICES

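### Lymphedema, a harm the protocol itself raises, is not systematically ascertained, so an absence of recorded cases could not support a safety statement about it

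*Combined protocol and SAP*

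**What the plan says.** The primary objective in section 3.1 is "Determine safety and feasibility measured by exercise compliance", and the hypothesis is that the regimen "is safe and feasible in women and may improve functional mobility, body composition, and resting metabolic rate". Section 3.4 calls the study one of feasibility and safety.

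Lymphedema appears in the background, section 3.2. Load progression in most earlier studies "has been slow with low loads to avoid exacerbating lymphedema", and the barriers to weight training are described as "including concerns of safety and lymphedema risk". The next sentence says that "these risks have been largely disproved by the current available research".

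Apart from titles in the reference list, lymphedema is not mentioned again. It is absent from:
- the eligibility criteria (section 4);
- Table 1 and the baseline assessments (sections 6 and 6.2);
- the safety analysis (7.1) and adverse-event reporting (8.1);
- the list of stored data (10.4), which does name "Surgical procedure for breast cancer or orthopedic procedures".

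The scheduled questionnaires are "EQ-5D-5L, and Leisure-Time Exercise Questionnaire SOC". Their text in Appendices II and IV has no swelling item; the closest is general pain or discomfort. A breast-specific instrument is in the abbreviation list but is not scheduled. The bioimpedance device is described for body composition and metabolic rate only.

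On adverse events, 7.1 states: "Accidental disclosure of confidentiality is the only adverse event that would occur". Section 8.1 nevertheless collects all adverse events found in the medical record and on the adverse-event form, from consent to the program completion visit.

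**The concern.** The study may be cited as evidence that heavy lifting is safe after breast cancer treatment. A reader of that report will look for the harm that the protocol says held loads down in earlier programs. If the report shows no cases, the reader needs to know whether women were asked.

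Under the plan they need not be. A case is recorded only if a woman volunteers it or a clinician notes it, and someone then enters it, in a study whose safety section says to expect nothing of the kind. A case that is recorded may also be hard to interpret: without a baseline answer on swelling, it may not be possible to call it new, worse or long-standing.

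**Working it through.** **The plan's own figure.** The only design calculation is in 7.2: a lower bound of 0.56 for 40 patients at a completion rate of 0.7. With 28/40, the exact (Clopper-Pearson) lower limit of a two-sided 90% interval is 0.5597, so the figure reproduces on that reading. It concerns attendance and carries no information on lymphedema. The documents give no lymphedema rate and no safety threshold.

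**What each route would catch.**

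| Route | Where | Limit for lymphedema |
|---|---|---|
| History and physical | Table 1, 6.1, 6.2 | Screening or baseline only; lymphedema not named |
| Comorbidity field | 10.4 | Generic; completeness unknown |
| Questionnaires | Appendices II, IV | No swelling item |
| Observation at workouts | 7.1 | Directed at adjusting exercise; no recorded lymphedema item |
| Adverse-event collection | 8.1 | Counts charted cases; ends at program completion |
| 1-year assessment | Table 1 | Outside the adverse-event window; no lymphedema item |

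**What zero cases could show.** Inputs: n = 40 (3.5 and 7.2) and zero observed cases (illustration). If every woman is checked, the upper limit solves (1 − p)^40 = α, so p = 1 − α^(1/40):
- one-sided 95%: 1 − 0.05^(1/40) = 0.072, or 7.2%;
- two-sided 95%: 1 − 0.025^(1/40) = 0.088, or 8.8%.

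**Effect of incomplete capture.** If only a fraction c of cases reaches the record, zero recorded cases bounds c × p, so the limit for p is the limit above divided by c. The documents give no value for c, so a range is shown (one-sided 95%):
- c = 0.75: 0.0722 / 0.75 = 0.096, or 9.6%;
- c = 0.50: 0.0722 / 0.50 = 0.144, or 14.4%;
- c = 0.25: 0.0722 / 0.25 = 0.289, or 28.9%.

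Since c is unknown under the plan, none of these could be reported as the study's limit.

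**Would asking be informative at this size?** The chance of at least one case among 40 women, 1 − (1 − p)^40, is 33%, 55%, 87% or 99% at assumed true rates of 1%, 2%, 5% or 10%. Asking would therefore probably reveal a rate of 5% or more, but could easily miss a rate of 1% or 2%.

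**The case against.** There are four serious objections.

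1. *Adverse events are already collected.* This is correct. A reader might infer that lymphedema is not counted at all, but 8.1 does not support that: a case charted before program completion would be counted. The sentence in 7.1 is a forecast and does not cancel that collection. What remains is that nobody is told to ask, and collection stops before the 1-year assessment.

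2. *The protocol regards the risk as largely settled.* Section 3.2 says so, and reports that several studies found no increase and possibly an improvement. It also lists lymphedema beside general safety concerns, so reading it as the single barrier goes too far. But the reassurance is limited by the protocol's own account. Section 3.2 says that most earlier studies progressed slowly with low loads, and one study cited for the absence of increase is the home-based program it describes as using light weights. Section 3.3 describes most exercise studies as aerobic or low to moderate intensity, and reports little data on compound closed-chain training. Mostly low-load evidence cannot fully stand in for asking women who lift heavy loads.

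3. *A baseline route exists.* A reader might infer that no baseline status could be known. The history, the chart review in 6.1 and the comorbidity field could hold a prior diagnosis. They do not name lymphedema, so the route is partial.

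4. *Lymphedema is only one harm.* This stands. Section 3.1 measures safety by compliance, and no harm endpoint is defined for anything, including the musculoskeletal events that 3.2 reports from earlier studies. Lymphedema is one clear instance of a wider gap.

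**Conclusion.** The point holds as a gap in ascertainment. It is not evidence that the regimen provokes lymphedema, or that cases would be hidden. The attendance endpoint is unaffected. What the study could not do is let an absence of recorded cases stand as evidence of safety for this harm.

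The limits of 7.2% and 8.8% are the best that 40 women with no cases could give, and they assume that all 40 are asked and answer. The 9.6% to 28.9% range rests on assumed capture fractions and only illustrates how quickly the limit loosens. Better ascertainment would make a limit valid; it would not make it tight. The change should be made, because baseline status is hard to reconstruct once training has begun.

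**What to change.** - Add a separate short study form at the existing baseline, completion and 1-year visits. Keep the items out of the EQ-5D-5L and Godin questionnaires, which are fixed, scored instruments.
- Use two yes/no items: arm, hand or chest swelling (present, at baseline; new or worse since the last visit, thereafter), and any lymphedema diagnosis or treatment.
- Name lymphedema as a solicited event in 7.1, and reconcile the 7.1 sentence on confidentiality with the collection described in 8.1.
- Report the number of women with new or worse swelling with an exact 95% CI, using the women who answered as the denominator.
- Report the 1-year answers separately, or extend the 8.1 window to cover them. Under 10.2 they can come only from women who reconsent, so that denominator may be below 40.

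No visit, device or arm measurement is added. The costs are a short amendment with IRB approval (10.5), about a minute per visit, and one extra table. Self-report is less precise than measurement, and intervals at n = 40 will stay wide.

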The exercise program will last three months. The initial exercise schema was developed by the PI and exercise personnel. Throughout the exercise program, participants will continuously be assessed via load lifted calculations and observations of exercise mechanics, both of which will impact increases in load and exercise difficulty during the program, as per SOC.

6.4 Follow-up Period:

There will be no follow-up once an individual completes the study.

6.5 Early Withdrawal of Subject(s):

If at any time the constraints of this protocol are detrimental to the patient's health and/or the patient no longer wishes to continue in the study, the patient will be removed from the protocol follow-up. In this event the reason(s) for discontinuation of study participation will be noted by the PI in the record. Data acquired up until that point will be retained for analyses.

There will be a SOC follow up assessment 1 year after the completion of the exercise program. The data from the SOC assessment will be used for research purposes.

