6.5.2 Follow-up Requirements for Early Discontinuation

There will be no follow-up once an individual completes or withdraws from the study. Data that was already collected from participants who discontinue will be used in analyses up to the point of discontinuation, and attempts will be made to collect data from participants at appropriate time points even after discontinuation of the exercise program.

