6.5.3 Replacement of Early Withdrawal(s)

Subjects who prematurely withdraw will not be replaced unless withdrawal occurs prior to initiation of the exercise regimen.

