7.2 Analysis of Adherence

The primary feasibility endpoint will be session attendance and will be calculated as the proportion of participants completing at least 75% of the planned exercise sessions. Dropout rate, defined as individuals who quit the workout regimen altogether, is 20%. It is assumed that the rate of attendance will be similar in this pilot study. The 90% lower confidence bound (LCB) for the proportion of patients completing at least 75% of exercise sessions will be constructed. A 90% LCB $\geq .56$ will be considered a success (that is, the proportion of patients successfully completing the exercise regimen is at least 0.56 with 90% confidence). With 40 patients studied, a 90% LCB of 0.56 is associated with a completion rate of 0.7. Data from all participants will be analyzed for anthropometric, metabolic, fitness and QOL regardless of attendance level but a subgroup analysis will be performed using data from participants with $\geq 75\%$ attendance.

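### The denominator of the primary completion rate is not fixed, so up to three women who fail the endpoint could be left out and a near-threshold result turned into a success

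*Combined protocol and SAP*

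**What the plan says.** Section 3.5 sets an accrual goal of 43 women "to achieve a sample size of 40 subjects, allowing for enrolled subjects who are unable to be complete the exercise program". The stated reason for the three extra places is women who cannot complete the program.

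Section 7.2 defines the primary feasibility endpoint as session attendance, "calculated as the proportion of participants completing at least 75% of the planned exercise sessions". Success is a 90% lower confidence bound (LCB) of at least 0.56, calibrated as follows: "With 40 patients studied, a 90% LCB of 0.56 is associated with a completion rate of 0.7". The same section gives a dropout figure: "Dropout rate, defined as individuals who quit the workout regimen altogether, is 20" per cent.

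Three other sections deal with women who stop:

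- Section 6.5, on withdrawal: "Data acquired up until that point will be retained for analyses".
- Section 6.5.2: "Data that was already collected from participants who discontinue will be used in analyses up to the point of discontinuation".
- Section 6.5.3: "Subjects who prematurely withdraw will not be replaced unless withdrawal occurs prior to initiation of the exercise regimen".

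Section 7.2 also says that all participants are analysed whatever their attendance, but that sentence covers the anthropometric, metabolic, fitness and QOL data and not the attendance endpoint.

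**The concern.** In most trials, adding a few places for women who do not finish only protects the sample size. Here, finishing is the outcome. A woman who cannot complete the program is normally a failure on the primary endpoint, so reaching 40 by allowing for such women treats endpoint failures as lost sample. Section 7.2 then applies the success rule to 40.

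The retention and replacement rules point the other way, but they do not settle the matter. Keeping a woman's data up to the day she stops does not say that she counts as not completing. A rule on replacement is not a rule on analysis. All enrolled, all who start, and the 40 left after the allowance are each compatible with the text.

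This is the only formal decision rule in the plan. If the denominator stays open, it could be chosen after attendance is known. Leaving out women who fell short of 75% can only move the result towards declaring feasibility.

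**Working it through.** **Inputs.** From 3.5: 43 enrolled, 40 in the sample, so 43 − 40 = 3 places. From 7.2: threshold 0.56, 90% confidence, planned rate 0.70 on 40 (28 completers, 12 failures), dropout 20%. Neither the interval method nor the number of sides is stated, so both a 10% and a 5% lower tail are shown.

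**The plan's own figure.** The exact (Clopper-Pearson) lower bound for x completers out of n is the α quantile of Beta(x, n − x + 1). For 28/40 it is 0.5884 with α = 0.10 and 0.5597 with α = 0.05. The second rounds to the plan's 0.56. Strictly it lies just below 0.56, so on that method 28/40 passes only after rounding.

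**Bounds with 40 and with 43 in the denominator**

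| Completers / n | Rate | Bound, 10% tail | Bound, 5% tail |
|---|---|---|---|
| 27/40 | 0.675 | 0.5625 | 0.5337 |
| 28/40 | 0.700 | 0.5884 | 0.5597 |
| 29/40 | 0.725 | 0.6147 | 0.5861 |
| 28/43 | 0.651 | 0.5425 | 0.5148 |
| 29/43 | 0.674 | 0.5664 | 0.5387 |
| 30/43 | 0.698 | 0.5905 | 0.5629 |

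The smallest passing count on 40 is 27 (10% tail), 28 (5%, rounded) or 29 (5%, unrounded). On 43 it is 29, 30 and 30. The results that pass on 40 and fail on 43 are therefore 27 or 28 completers, 28 or 29 completers, and 29 completers only.

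**False success at a true rate of 0.56.** If 43 start and exactly three failures are removed, the number of completers X is still Bin(43, 0.56), but it is judged against the cut-off for 40.

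| Rule | Three failures dropped from 43 | All 43 counted | 40 start, all counted |
|---|---|---|---|
| 10% tail | P(X ≥ 27) = 23.0% | P(X ≥ 29) = 8.6% | P(X ≥ 27) = 9.5% |
| 5% tail, rounded | P(X ≥ 28) = 14.7% | P(X ≥ 30) = 4.6% | P(X ≥ 28) = 5.0% |
| 5% tail, unrounded | P(X ≥ 29) = 8.6% | P(X ≥ 30) = 4.6% | P(X ≥ 29) = 2.4% |

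**A less extreme model.** Suppose each of the 43 is lost with probability 3/43, and the lost women are all non-completers. The number left is Bin(43, 40/43), and the completion rate among them is 0.56 / (40/43) = 0.602. Applying the exact bound to whatever number is left gives false success of 18.4% (10% tail) or 9.5% (5% tail, unrounded).

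**Whom do the three places cover?** The allowance is 3/43 = 7.0%. The dropout figure in 7.2 implies 0.20 × 43 = 8.6 women. At a 20% rate, the chance that three or fewer of 43 quit is P(Bin(43, 0.20) ≤ 3) = 1.8%. The allowance cannot be meant to cover all expected quitters, and the plan does not say which women it does cover.

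**The case against.** The strongest reply is that section 3.5 is only a recruitment statement. It orders no exclusion, and the 40 in section 7.2 is a planning illustration. Section 6.5.3 replaces women only before exercise starts, so the three places may simply cover women who never start, and then nothing changes. The planned 28/40 already contains 12 failures, which fits a plan that counts quitters. The mismatch between three places and 8.6 expected dropouts also suggests that the two figures describe different women. All of this is fair, and it makes the benign reading plausible. It does not make it the stated rule: section 3.5 gives inability to complete, not failure to start, as the reason.

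The second reply is that the error rates are worst cases. This stands in part. The figures of 23.0% and 14.7% need all 43 to start and three women below 75% to be removed. A woman could reach 75% of sessions and then stop, in which case she is not a failure. The largest figure also uses the 10% tail, whereas only the 5% tail matches the plan's 0.56 under the exact method. With 5% unrounded, the inflated rates of 8.6% and 9.5% remain below 10%. Part of the spread thus comes from the unstated tail and rounding, which is a separate gap.

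The third reply is that choosing the denominator after the fact is a possibility and not a plan. That is true, and it is the reason to fix the denominator beforehand.

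**Conclusion.** The concern holds. The primary denominator is not defined, section 3.5 taken literally conflicts with sections 6.5 to 6.5.3, and three women are enough to reverse the decision at or next to the plan's own benchmark of 28 completers. Leaving out three failures multiplies the chance of false success at a true rate of 0.56 by roughly two to three, compared with counting all 43.

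This size is conditional. It assumes that the women set aside started the regimen and did not reach 75% of sessions, and that exact bounds are used. Three is the difference between 43 and 40, not a cap that the plan states. The finding is that the text permits this reading, not that the sponsor intends it. It should be fixed before attendance is analysed. Confidence is high that the definition is missing.

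**What to change.** In sections 3.5 and 7.2, state: *The primary denominator is every participant who starts the exercise regimen. Participants who quit, withdraw or are withdrawn before reaching 75% of the planned sessions count as not completing.* In 3.5, limit the three extra places to withdrawals before the first session, in line with 6.5.3. A rate among women who did not withdraw can be added as a descriptive figure.

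State the cut-off for the number who start. With exact bounds:

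| Starters | 10% tail | 5% tail |
|---|---|---|
| 40 | 27 | 29 (28 if 0.5597 is rounded to 0.56) |
| 43 | 29 | 30 |

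The cost is small. Attendance is already recorded at every session, so no new data are needed. The reported completion rate may be slightly lower. Power at a true rate of 0.70 is not lost by counting all starters:

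- 10% tail: 70.8% with 29/43, against 70.3% with 27/40.
- 5% tail: 58.7% with 30/43, against 57.7% with 28/40 (rounded) or 44.1% with 29/40 (unrounded).

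What is given up is only the extra chance of success from dropping three failures, which would have raised these figures to 88.3% (cut-off 27) or 80.8% (cut-off 28).
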